4.1 **If you are requesting additional or other modifications to the protocol, please describe these changes. Also, attach a copy of your tracked/revised documents or new documents associated with this modification.**

Describe the proposed modification(s):

We request permission to amend the protocol to remove the 600 mg/day dose of mifepristone from the remainder of the study. We will focus on 1200 mg/day of mifepristone versus placebo. The decision to remove the lower dose of mifepristone is based on literature in psychotic depression showing a plasma: dose response with plasma concentrations above threshold associated with clinical response; plasma concentration above threshold is more likely to be

achieved with 1200 mg/day than with 600 mg/day. To date, both doses have been very well tolerated in our study population and we believe that the 1200 mg dose would provide the most adequate test of our study hypotheses.

4.2 *Will the proposed modifications change the population, purpose or procedures?

Yes No

If yes, outline those changes:

4.3 *Will the requested modification(s) change the risks or benefits to subjects?

Yes No

If Yes, explain:

4.4 *Will the proposed changes require notification to subjects in a revised informed consent form or addendum?

Yes No

5.0

ATTACHMENTS

Attach a copy of any revised or new documents associated with this modification. For updated protocols and IDBs include a summary of the changes and sponsor letter.
(Highlight or track the changes in a revised document).

5.1 Consent Revisions or New Consent Form:

Version	Title	Category	Language	Expiration Date	Consent Outcome	Checked Out	View Document
1.35	Revised Consent. 1.9.18 (Clean /Approved)		English	05/11 /2018	Void		 287.71 KB

5.2 Normal Blood Donor Service consent form:

Version	Title	Category	Language	Expiration Date	Consent Outcome	Checked Out	View Document
No Consent(s) have been attached to this form.							

5.3 Attach any other documents associated with this request:

Version	Sponsor Version	Title	Category	Expiration Date	Document Outcome	Checked Out	View Document
1.0		[name] CITI Certificates	Other				 2.11 MB

1.0	Blasely et al 2010	Other			 691.02 KB	
1.0	Blasely et al 2009	Other			 193.75 KB	

Scripps IRB

[name]
[name]

Office for the Protection of Research Subjects

Approval Notice (Modification)

Investigator: [name].

Department: The Scripps Research Institute – Dept. of Neuroscience

Approved

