Statistical Plan

Glucocorticoid Antagonist Treatment of Alcohol Use Disorder

From NIH Grant Application #AA023152

P.I. [name].

Submitted 2/7/2014

All analyses will be conducted in the intention-to-treat sample with $p<0.05$ for two-tailed tests of significance. Demographics and baseline measures will be examined for differences between treatment groups and tested individually for correlation with each outcome. Any baseline variable significantly associated with outcome or differing between treatment groups will be included in subsequent analyses as a covariate. Trend dose effects will be determined using single or multi parameter tests of Mixed Effect Model (MEM) effects, as required. All MEMs are repeated measures centered on the relevant time period. Time, treatment, and time x treatment will be evaluated as fixed effects in each model.

Mifepristone plasma concentration and baseline drinking levels were significant predictors of response in our Proof of Concept (POC) study and will be evaluated as predictors in the proposed study. Sex, age, age of onset and family history of alcoholism will be examined as covariates of response because of a potential association with cortisol in the case of the latter 3 variables and to assess differential treatment response for males and females, given mifepristone's antiprogestrone effects, and the trend for females to have better drinking outcome in our POC study. Motivation, e.g., to have abstinence as a treatment goal, will be examined as a non-specific predictor of treatment outcome. Potential pharmacogenetic predictors of response will be evaluated on an exploratory basis.

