Furthermore, a collaboration with [name], Director, Neurogenetics Lab, NIAAA, will permit an exploratory evaluation of genetic predictors of response; the high affinity of mifepristone for the glucocorticoid receptor makes mifepristone a good candidate for pharmacogenetic analysis that may guide future studies and clinical applications.

GENERAL INVESTIGATIONAL PLAN

SUBJECTS

Sample Size

Power and sample size estimates are based on the change in the number of drinks per week found in our POC study that involved 1-week of mifepristone 600 mg/d vs placebo in 50 subjects with AUD and in our 12-week clinical trial of gabapentin 900mg, 1800mg and placebo in 150 subjects with AUD.² Repeated measures ANCOVA performed on the change in number of

drinks per week from baseline through Week 5 in the POC study found significant ($F=3.82$, $df=2$, $p=0.03$) slope effects between mifepristone (-9.19, SEM 7.5) and placebo (+3.62, SEM 7.5), yielding a Cohen's $d=0.485$ (medium effect size). Continuous outcomes will be assessed for trend dose effects. Based on estimates of change of 0, -2.2 and -6.7 (SE 1.6) drinks per week for placebo, 900mg and 1800mg, respectively, in our gabapentin study, the test for linear trend contrast resulted in highly significant ($p<0.001$) linear trends with post hoc power at least 99% at the target alpha. Power calculation of cumulative mean drinks per week vs. dose with a planned linear contrast indicates that with 50 subjects per arm (placebo, low dose, high dose), and means which decrease by at least 32% as dose increases, we achieve 91% power to detect a non-zero contrast of the means versus the alternative that contrast is zero using an F test. These calculations assume an alpha=0.05, a common SD \pm 12, and hypothesized means of approximately 16, 11 and 8 drinks per week based on the gabapentin data. Estimating early termination by approximately 40% subjects based on clinical trials of similar design,^{2,3} the same power analysis for a conservative total of 30 subjects per arm indicates 82% power to test the interactive term (week*treatment) at the alpha of 0.05.

Subject Characteristics

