- *Current use of drugs that are CYP3A substrates and inhibitors (such as calcium channel blockers, azole antifungals, macrolide antibiotics, erythromycin, protease inhibitors) due to risk of interactions with mifepristone; CYP3A inducers (such as rifampin, rifabutin, rifapentine, phenobarbital, phenytoin, carbamazepine, and St. John's wort), which may decrease mifepristone exposure and possibly compromise efficacy or consuming grapefruit juice or chronic use of drugs that are CYP2C8/2C9 substrates (such as NSAIDs, warfarin, and repaglinide), or as determined by the Study Physician*
- *No fixed domicile and/or no availability by home or mobile telephone*
- *Treatment mandated by a legal authority*

Subject Recruitment and Retention

This is the first test of the clinical efficacy of mifepristone for AUD, and as such, requires recruiting individuals with AUD who are both treatment-seekers and free from clinically significant medical and psychiatric disorders or use of concomitant medications that could influence study outcomes. Our experience conducting two N=150, 12-week clinical trials in AUD

with similar admission criteria at Scripps reliably shows we must recruit about 5 subjects for each subject who is successfully randomized, resulting in a rate of randomization of approximately 33 subjects per year. This rate of randomization is consistent with the average rate of 30-36 subjects randomized annually by single sites in recent AUD trials with similarly restrictive admission criteria.

Per procedures established by NIAAA's Clinical Investigations Group,⁴ progressive incentive payments will be provided for attendance and completion of study assessments to enhance compliance with study procedures and retention. Subjects will earn a base rate starting at \$25 that will increase by \$5 for each subsequent consecutive visit. The 4 weekly phone calls will be compensated at a flat rate of \$10 each. Perfect attendance and participation in 4 phone calls will result in a subject earning \$590 over the 12 weeks of study and follow up.

PROCEDURES

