Genetic Indicators of Mifepristone Effects Saliva samples will be collected using Oragene DNA (OG-500) 2 ml saliva kits (DNA Genotek, Inc) and genotyped on the Illumina Human Omni Express Exome beadchip, with analysis limited to selected candidate genes. Differences in response to mifepristone may also be reflected in cellular differences in response to the drug and to cortisol. To study this, blood samples will be collected and sent by same day transport to [name] Biochemical Genetics Laboratory at UCSD, which is located less than 1 mile from our lab and where peripheral white blood cells (PWBC's) will be extracted and cryopreserved. PWBCs will be isolated by density centrifugation through Nycoprep from whole blood (2 x 8ml) stabilized with acid citrate dextrose and stored at -140°C in tissue culture medium supplemented with 10% DMSO to maintain viability. [name] lab at NIAAA will generate lymphoblastoid cell lines and iPSC lines from cryopreserved PWBCs. Cell lines established from high and low responders to mifepristone will be analyzed for gene expression and methylation differences by RNA-seq and whole genome methylation analysis (Week 0, samples collected by Medical Technician). Cortisol and ACTH Blood is collected, spun, prepared, frozen and stored in [name] lab for periodic batch analysis in the [name]' lab using Enzyme Linked ImmunoSorbent Assay (ELISA) kits to provide quantitative determination of ACTH and cortisol in plasma (Weeks 0, 1, 2, 4, 8 and 12).

Safety Measures:

Breath Alcohol Concentrations (BAC) Subjects are informed prior to the screening visit that if they present with positive BAC's, they will not be paid and will be rescheduled, and have to wait until BAC is normal or will be accompanied home by a friend or taxi driver (beginning of every study visit, Research Nurse, 2 minutes). Adverse Event- Case Report form records each adverse event and onset, duration, severity, relation to study medication and clinical action (every study visit, Research Nurse, 5 minutes). Urine screen for illicit drug use (Weeks -1, 1, 4, 8 and 12).

PHARMACOTHERAPY CONDITIONS AND MEDICATIONS DISPENSED

Pharmacotherapy Conditions

Simple randomization procedures will be followed to randomly assign subjects to double-blind treatment with 600 mg/d or 1200 mg/d mifepristone or matched placebo in a 1:1:1 ratio, using a computer-generated randomization code provided by our laboratory biostatistician. Dose titration is not indicated.

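### After 600 mg closes, the SAP has no enrolment-period term, so 600 mg comparisons, multi-parameter tests and dose-response shape are open to calendar-time bias (the linear contrast is not, at 1:1)

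*Combined protocol and SAP*

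**What the plan says.** **Design as planned.** The protocol (Pharmacotherapy Conditions) assigns subjects by simple randomisation to 600 mg, 1200 mg "or matched placebo in a 1:1:1 ratio, using a computer-generated randomization code". The Sample Size section plans 50 per arm and a linear contrast of mean drinks per week across the three doses.

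**Amendment.** Item 4.1 of the Request for Modification/Amendment asks to "remove the 600 mg/day dose of mifepristone from the remainder of the study" and adds: "We will focus on 1200 mg/day of mifepristone versus placebo". Some subjects had already taken 600 mg, because the same item reports: "To date, both doses have been very well tolerated in our study population". It gives no closure count, revised total, new allocation ratio or rule for analysing the 600 mg subjects already randomised.

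**Analysis.** The SAP, submitted in February 2014, predates the amendment. It uses the intention-to-treat sample throughout and fits repeated-measures mixed models with time, treatment and their interaction as fixed effects. Time here is study time, not calendar time. On dose it says: "Trend dose effects will be determined using single or multi parameter tests of Mixed Effect Model (MEM) effects, as required". Baseline variables that are associated with outcome or differ between groups become covariates; enrolment date or period is not named.

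**Duration.** Subject Recruitment and Retention expects about five recruited per subject randomised, "resulting in a rate of randomization of approximately 33 subjects per year". For 150 subjects that is 150/33 = 4.5 years.

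**The concern.** While three arms are open, randomisation makes 600 mg and placebo comparable. After closure, every new subject goes to placebo or 1200 mg and none to 600 mg. All 600 mg subjects therefore come from the early period, while the other two arms span both. A model of the full sample without a period term pools early and late placebo, so part of the 600 mg comparison is no longer protected by randomisation.

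If drinking outcomes change over several years of accrual, through case mix, recruitment sources, staff or the delivery of counselling, placebo and 1200 mg shift together and 600 mg does not. That can appear as a 600 mg effect, or as curvature in the dose response. What is at stake is what the trial reports about 600 mg and the validity of any test that uses the 600 mg mean. Without a written rule, the choice between all placebo and concurrent placebo could be made after unblinding.

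**Working it through.** **1. Which planned test uses the 600 mg mean?** Inputs from Sample Size: means 16, 11 and 8, SD 12, 50 per arm, alpha 0.05; two-sided from the SAP. With equally spaced doses (0, 600, 1200) the linear contrast is (-1, 0, +1):

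- difference = 16 - 8 = 8; SE = 12 x sqrt(1/50 + 1/50) = 2.4
- noncentral t, 147 df: power 91.2%, which reproduces the stated 91%
- a 2-df F test on the same inputs gives 85.6%, so it is not the source of the 91%

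The quantified dose test gives 600 mg zero weight. It is in effect 1200 mg versus placebo. A multi-parameter test, which the SAP also allows, does use the 600 mg mean.

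**2. Assumptions for size.** Total 150; N0 = 90, 100 or 120 randomised before closure; 1:1 afterwards; uniform accrual; SD 12; no drug effect; drift of 4 drinks per week. Only the SD and the planned total of 150 come from the documents. The range for N0 is rough. The protocol is dated July 2014 and the amendment attaches a consent labelled 1.9.18. At 33 a year, a start between mid-2014 and mid-2015 (assumed) gives 3.5 x 33 = 116 down to 2.5 x 33 = 83 subjects.

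**3. Formulas.**

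- 600 mg n: k = N0/3
- placebo n: p = k + (150 - N0)/2
- late share of placebo: s = (p - k)/p
- bias, step at closure: 4s
- bias, linear drift: early and late subjects differ in mean enrolment position by (N0 + 150)/2 - N0/2 = 75 of 150, i.e. half of accrual, so 4 x 0.5 x s = 2s
- SE = 12 x sqrt(1/k + 1/p)
- type I error = Phi(-1.96 + bias/SE) + Phi(-1.96 - bias/SE)

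**4. Results, 600 mg versus all placebo.**

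| N0 | k | p | s | SE | Step: bias, type I | Linear: bias, type I |
|---|---|---|---|---|---|---|
| 90 | 30 | 60 | 50% | 2.68 | 2.0, 11.6% | 1.0, 6.6% |
| 100 | 33.3 | 58.3 | 43% | 2.61 | 1.71, 10.1% | 0.86, 6.2% |
| 120 | 40 | 55 | 27% | 2.49 | 1.09, 7.2% | 0.55, 5.5% |

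**5. Tests using all three means (step of 4).**

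- 2-df treatment test: noncentrality = sum of n x (arm shift - weighted mean shift)^2 / 144. At N0 = 100 the weighted mean shift is 1.71 x 116.7/150 = 1.33, so noncentrality = (116.7 x 0.38^2 + 33.3 x 1.33^2)/144 = 0.53 and type I error is 9.2% (10.4% at N0 = 90, 6.9% at 120).
- Curvature contrast (1, -2, 1): at N0 = 100 bias = 2 x 1.71 = 3.43 and SE = 12 x sqrt(1/58.3 + 4/33.3 + 1/58.3) = 4.71. Type I error is 11.2% (12.9% at 90, 7.8% at 120).

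**6. Wider closure range, by simulation.** 4,000 runs per scenario, closure after 25%, 50% or 75% of randomisations, linear drift of 4. The late share of placebo is 83%, 60% and 32%, and type I error for 600 mg versus placebo is 6.7%, 6.8% and 5.5%. With drifts of 2, 4 and 6, the linear contrast had bias within 0.04 and type I error of 4.8% to 5.7% throughout.

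**7. If the ratio changes.** Suppose 2:1 in favour of 1200 mg after closure (assumed), N0 = 100, step of 4. The late share is 33.3/66.7 = 50% on 1200 mg and 16.7/50 = 33% on placebo. 1200 mg versus placebo then shifts by 4 x (0.50 - 0.33) = 0.67 drinks per week (0.69 at N0 = 90, 0.53 at 120).

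**The case against.** The best defence is that the exposure is narrow. Neither document specifies a 600 mg versus placebo test, and the amendment moves the focus to 1200 mg versus placebo. The one dose test with a power figure is unbiased at 1:1. The documents give no evidence of drift. The trial is single-site with manual-guided counselling, and the SAP's covariate rule could absorb some change in case mix. All of this stands, and it limits the point. It does not remove it: the SAP allows multi-parameter tests, the 600 mg subjects stay in the intention-to-treat sample, and baseline covariates do not capture changes in staff or in how counselling is delivered.

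Four stronger readings are tempting and not supported:

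- *The planned dose trend is biased.* The contrast that reproduces 91% gives 600 mg no weight. A fitted dose slope behaves the same way when placebo and 1200 mg numbers are about equal.
- *600 mg is compared only with later placebo subjects.* At N0 = 100, 33 of 58 placebo subjects (57%) are concurrent.
- *The false-positive rate is about 10%.* That needs the whole 4 drinks per week to arrive as a step at closure. The gradual version gives about 6%.
- *The arm was closed because of its own results.* The stated reason is external: "The decision to remove the lower dose of mifepristone is based on literature in psychotic depression".

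**Conclusion.** The point holds in limited form. The current text lets non-concurrent subjects into any 600 mg versus placebo comparison, any 2-df treatment or time x treatment test, and any reading of dose-response shape, without adjustment. Bias needs a real calendar trend. Its sign is unknown, and its size is the drift multiplied by the late share of placebo (step) or by half that share (linear). The closure count, the 1:1 continuation and the drift of 4 drinks per week behind the illustration are all assumptions.

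The linear contrast and 1200 mg versus placebo are sound provided those arms keep a constant ratio, which the amendment leaves unstated. This is a worthwhile low-cost correction to the SAP, not a threat to the trial's main comparison.

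**What to change.** Update the SAP, before unblinding, to say:

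1. Each mixed model includes enrolment period (randomised before or after 600 mg closed) as a fixed factor, plus its interaction with study time wherever time x treatment is tested.
2. Any 600 mg versus placebo estimate uses placebo subjects randomised while 600 mg was open, or the period-adjusted model. The adjusted model also assumes that the 1200 mg effect is the same in both periods; the concurrent-only comparison does not.
3. Multi-parameter tests and statements on shape come from the period-adjusted model.
4. 1200 mg versus placebo and the linear contrast keep all subjects, adjusted for period.
5. The allocation ratio after closure, the revised total and the date of closure are stated.

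**Cost, at N0 = 100 and SD 12.** The work is a short SAP amendment and one variable built from the randomisation date. For 600 mg versus placebo, the SE rises from 2.61 to 2.78 period-adjusted, or to 12 x sqrt(2/33.3) = 2.94 with concurrent placebo only. For 1200 mg versus placebo it stays at 12 x sqrt(2/58.3) = 2.22, because period is balanced across those two arms at 1:1.

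Do not restrict the linear contrast to subjects randomised before closure. With means of 16 and 8, its power would fall from about 95% (58 per arm) to about 77% (33 per arm), with no bias removed at 1:1.
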